9.2.2. Prohibited Medications

Commercial OCA therapy (if available) is prohibited while on investigational product, and if prescribed during the course of the study, the Investigator should be cognizant of the possibility of double dosing. Patients who initiate with commercial OCA therapy must discontinue investigational product and are expected to continue through the end of the study (see [Section 8.4.1](#)). Fibrin acid derivatives (ie, fibrates such as fenofibrate and bezafibrate) are also prohibited while on investigational product.

9.3. Treatment Compliance

The Investigator should assess the patient's compliance with dosing of investigational product at each study visit, and confirm by conducting investigational product accountability (ie, count of returned tablets).

Patients should be instructed to retain all bottles of investigational product, even if empty, and to return them to the Investigator at the indicated visits ([Table 1](#)). The Investigator or designee should perform investigational product accountability (ie, count of returned tablets) and, if applicable, follow-up with the patient to retrieve any investigational product bottles that have not been returned.

If the Investigator has concerns about a patient's dosing compliance, he or she should discuss this with the patient, assess the reasons for noncompliance and the likelihood that the patient will remain noncompliant, and notify the Sponsor accordingly.

9.4. Randomization and Blinding

9.4.1. Methods of Assigning Patients to Treatment Groups

This study will be conducted in a double-blind, placebo-controlled manner. Enrolled patients who meet all eligibility requirements will be randomized in a 1:1 ratio to 1 of 2 treatment groups: placebo or OCA based on a predefined randomization code (generated by Sponsor or designee) using an interactive web response system (IWRS), which the Sponsor intends will serve as a computer-based patient registration system at Screening and Day 1.

Randomization will be stratified by CP class (CP-B or CP-C). Baseline MELD scores will be monitored on an ongoing basis to ensure adequate distribution of MELD scores. The IWRS will

serve as the investigational product inventory and management system and may be integrated with the study database.

The Investigator or designee will be required to register the patient in the IWRS and may be prompted to provide patient data necessary to properly randomize and allocate the patient to treatment. A randomization number will be assigned and investigational product (OCA or placebo) dispensing information will be provided (eg, bottle numbers allocated) while maintaining the study blind.

9.4.2. Blinding

The Sponsor, patients, Investigator, and study site staff will be blinded to the patient's treatment allocation during the patient's participation in the double-blind phase of the study.

9.4.3. Emergency Unblinding Procedures

Treatment assignment for individual patients will be made available to the Investigator for medical emergency use only (such as unblinding which is necessary in order to treat a serious adverse event [SAE] through the IWRS system). When possible, the Medical Monitor should be consulted in the event that a medical emergency necessitates unblinding (ie, in situations where knowledge of the blinded treatment assignment is necessary for further medical management of the patient). If it is not reasonable to inform the Medical Monitor in advance of the unblinding, the Investigator must promptly document in the patient's record the rationale for unblinding and should subsequently contact the Medical Monitor to explain any premature unblinding of treatment assignment. Procedures for unblinding a patient's treatment will be provided separately to the Investigator. Similarly, if the Medical Monitor breaks the blind for an individual patient for the purpose of evaluating an emergent safety issue, the Medical Monitor will document within study documentation the rationale, circumstances, and the person or persons being informed about the unblinding.

The DMC will have access to the IWRS and will be able to unblind individual patients. Refer to [Section 15.8](#) for further details regarding DMC access to blinded and unblinded data. The DMC will document details about any unblinded patient data reviews in the closed session DMC minutes, which will be made available to the Sponsor only after the database is locked and the study is unblinded. Cases of premature unblinding, as noted above, will also be reviewed by the DMC.

Access to treatment assignments will also be made available to the designated Intercept staff responsible for expedited safety reporting of suspected unexpected serious adverse reactions (SUSARs) to the Regulatory Authorities.

9.5. Assignment of Site and Patient Numbers

9.5.1. Site Numbers

Each study site selected to participate in this study will be assigned a site number by the Sponsor. The site number will be used to categorize patient data and to identify the site and/or Investigator within study documents. This number will be recorded in the eCRF.

9.5.2. Patient Numbers

Patients are assigned using a unique 10-character identifier (AAA-BBBCCC), independent of the randomization number. The first 3 digits represent the last 3 digits of the protocol number, followed by a hyphen (AAA-). The next 3 digits represent the site number (BBB). The last 3 digits represent a unique screening number that is assigned in sequential order at each site starting with 001 (CCC).

9.6. Restrictions

Participation in another investigational product, biologic, or medical device study within 30 days prior to Screening and during the course of the study is prohibited. Previous exposure to OCA (as a study participant or received commercial OCA therapy) is allowed provided patients haven't taken OCA within 3 months prior to enrollment in this study.

9.6.1. Fasting Requirement at Study Visits

All patients must have been fasting for at least 8 hours prior to their Screening Visit and all subsequent study visits, as all analytes will be assayed in fasting blood or plasma samples. Water is permitted during the fasting period.

9.7. Visit Procedures

9.7.1. Visit Windows

Visit windows are specified in the Schedule of Study Procedures ([Table 1](#)). Visits should be based on Day 1 (not on the prior visit) unless stated otherwise. For example, Week 6 should ideally occur 6 calendar weeks (± 7 days) following Day 1.

9.7.2. Informed Consent Procedures

The Investigator or designee will explain the nature, purpose, possible risk, and benefit of the study to the patient and will provide him/her with a copy of the informed consent form (ICF). The patient will be given sufficient time to consider the study before deciding whether or not to participate. The patient will be informed that participation is voluntary and that her/his future medical treatment will not be compromised by participation in the study and that he or she can withdraw from the study at any time. The patient must be willing and able to provide written informed consent (on hard copies) before entering the study. The Investigator or a medically qualified designee is responsible for administering and documenting the written informed consent of the patient. The patient will be given a copy of the patient information sheet (PIS) and his/her signed and dated informed consent form (ICF).

9.7.3. Assessing Cirrhosis

Acceptable methods of confirming (via medical history) or assessing cirrhosis for purposes of the study are defined as a patient who has documented evidence or presence of one or more of the following cirrhosis indicators:

- Biopsy results consistent with PBC Stage 4 ([Ludwig 1978](#))

- Liver Stiffness as assessed by TE Value ≥ 16.9 kPa (Corpechot 2012)
- The presence of any of the following (unless exclusionary per Section 8.3) in the absence of acute liver failure:
 - Gastroesophageal varices
 - Ascites
 - Radiological evidence of cirrhosis (nodular liver or enlargement of portal vein and splenomegaly)
- Combined low platelet count ($<140\,000/\text{mm}^3$) with:
 - Persistent decrease in serum albumin, or
 - Elevation in prothrombin time /INR (not due to antithrombotic agent use), or
 - Elevated bilirubin ($2\times$ ULN)

9.7.4. Screening Procedures (14 days to 28 days prior to Day 1)

Informed consent must be obtained from the patient before performing any study-related procedures, including Screening procedures. The Screening Visit assessments must be performed ≥ 14 days but less than 28 days prior to Day 1 to determine whether the patient meets all the inclusion criteria and none of the exclusion criteria. Patients who do not fulfill all eligibility criteria will not be enrolled in the study. Patients may be rescreened after 2 months have elapsed from the date of their most recent screening visit procedure; however, all Screening procedures (including obtaining informed consent) should be repeated and a new three-digit Screening number assigned.

Screening Visit procedures are as follows:

- Verify that the patient has fasted for at least 8 hours.
 - Record fasting status in the source and eCRF
 - If the patient reports having eaten within 8 hours, document accordingly in the source and eCRF and remind the patient that fasting is required prior to all study visits.
- Collect medical history.
- Collect PBC history.
- Verify inclusion and exclusion criteria for eligibility.
- Perform a physical examination, including height, smoking and alcohol consumption history, and current habits for both.
- Assess and record vital signs and weight (oral temperature, sitting heart rate, respiratory rate, and sitting blood pressure).
- Assess and record any pretreatment-emergent AEs.
- Record prior (if within 30 days of Screening) and current concomitant medications.

- Perform a standard 12-lead electrocardiogram (ECG).
- Perform assessments for calculation of CP Score ([Section 14.1.1](#))
- Obtain blood samples for
 - Serum chemistry, hematology, and coagulation
 - Virology Screen (HCV and HBsAg)
- Obtain urine sample for urinalysis
- Perform a urine-based beta human chorionic gonadotropin (β -hCG) pregnancy test in females of childbearing potential.
- Instruct the patient to fast overnight (at least 8 hours) before the next visit (water is permitted).
- Record the visit in IWRS.
- Perform an ultrasound for HCC surveillance and evaluation of gallbladder status (if equipment is unavailable, sites should make every attempt to use available community referral sites). If an ultrasound has been done within 12 months of Screening, and a report/adequate data are available, a pretreatment ultrasound at Screening is not required. If the ultrasound cannot be performed at Screening (eg, device/technician unavailability, scheduling issues, etc), the procedure may be completed anytime within the screening visit window or on Day 1. Results from the screening ultrasound should be reviewed to assess possible exclusion criteria prior to randomization.

9.7.5. Day 1 Procedures (Randomization)

- Verify that the patient has fasted for at least 8 hours.
 - Record fasting status in the source and eCRF
 - If the patient reports having eaten within 8 hours, document accordingly in the source and eCRF and remind the patient that fasting is required prior to all study visits.
- Review inclusion and exclusion criteria for eligibility.
- Perform a physical examination.
- Review and record any non-study related medical or surgical treatment procedures and any medically relevant health care professional (HCP) or non-HCP related office visits that have occurred since the previous study visit.
- Assess and record vital signs and weight (oral temperature, sitting heart rate, respiratory rate, and sitting blood pressure).
- Assess and record any pretreatment-emergent AEs.
- Review and record prior concomitant medications.
- Perform assessments for calculation of CP Score ([Section 14.1.1](#)).

- Administer Quality of Life and Patient questionnaires ([Section 13.2.7](#)).
- Randomize the patient only if s/he meets all inclusion criteria and no exclusion criteria.
- Record the visit in IWRS and dispense investigational product
 - Instruct the patient to begin dosing on the day of the Day 1 Visit.
- Obtain urine sample for urinalysis
- Perform a urine-based β -hCG pregnancy test in females of childbearing potential.
- Obtain blood samples for
 - Serum chemistry, hematology, and coagulation
 - Markers of fibrosis (ELF [HA, P3NP, and TIMP 1])
 - Fasting PK assessment
 - Bile Acid/C4/FGF-19
- Perform TE using the Fibroscan[®] TE device. If the TE cannot be performed on Day 1 (eg, device/technician unavailability, scheduling issues, TE data is needed to inform cirrhosis assessment, etc.), the procedure may be completed within the Day 1 Visit window, (if data is needed for cirrhosis assessment) or as close as possible to the Day 1 Visit, preferably, after patient eligibility has been confirmed. Instruct the patient to take Day 1 dose on the day of this visit.
- If ultrasound for gallbladder assessment was not performed at Screening and the historic ultrasound is >12 months from Day 1, perform ultrasound.
- Schedule the next visit, reiterate dosing instructions, and advise the patient:
 - NOT to take investigational product on the morning of the next visit, and
 - To bring the investigational product bottle(s) to the visit
 - To fast overnight (at least 8 hours) prior to the next visit. Fasting is required prior to all study visits, but water is permitted.

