- ⁱ New investigational product bottles will be dispensed if the patient is up-titrated. Unless up-titrated, patients are expected to use up each investigational product bottle before a new bottle will be dispensed. No new bottles will be dispensed if dose frequency is changed. Patients will be instructed to begin dosing on Day 1, after completing all study assessments. Patients will be instructed to take investigational product at approximately the same time of day. Patients must be instructed to swallow the tablet whole; they must not chew, divide, or crush the tablet.
- ^j Dose titration of investigational product may occur starting after the Week 12 Visit, or any study visit thereafter for patients on all dosing regimens, based on tolerability and safety laboratory tests from the previous visit. Subsequent dose titration(s) may occur no earlier than 6 weeks after the previous dose titration and will be based on tolerability.
- ^k Urine β -hCG pregnancy tests must be performed in females of childbearing potential prior to entry and at every visit (except Week 3). If positive, a confirmatory blood test must be performed at the central laboratory. If the confirmatory blood test is also positive, the patient may not continue in the study. (Additional testing may be conducted where required, regionally).
- ^l MELD values will be calculated based on serum chemistry and coagulation values at each visit.
- ^m The patient will be given the option to return to the clinic the following morning for the 24-hour postdose PK sample or samples can be obtained by a home health care designee. Patients who are discontinued from investigational product prior to completion of the study are encouraged to continue to follow the regular visit schedule, with the exception of PK sampling.
- ⁿ The noninvasive radiological liver fibrosis measurement devices (such as, FibroScan[®] device [Echosens; Paris, France]) will be used at all study sites to collect hepatic stiffness measurements.
- ^o Patients will complete a TE/ELF and ultrasound assessment, every 6 months (± 2 weeks) after Week 48.
- ^p ECG and urinalysis will be done yearly (± 2 weeks) after Week 48 Visit.
- ^q Ultrasound will be conducted to enhance HCC surveillance. For all on study (eg, post-Day 1) ultrasounds: Unless HCC has already been confirmed by biopsy, a second confirmatory image (eg, MRI) should be obtained to confirm suspected HCC.

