8.2. Patient Inclusion Criteria

1. A definite or probable diagnosis of PBC (consistent with American Association for the Study of Liver Diseases [AASLD] and European Association for the Study of the Liver [EASL] Practice Guidelines [Lindor 2009, EASL 2009]), defined as having ≥ 2 of the following 3 diagnostic factors:
 - History of elevated ALP levels for at least 6 months
 - Positive antimitochondrial antibody (AMA) titer or if AMA negative or low titer ($\leq 1:80$), PBC-specific antibodies (anti-GP210 and/or anti-SP100) and/or antibodies against the major M2 components (PDC-E2, 2-oxo-glutaric acid dehydrogenase complex)
 - Liver biopsy consistent with PBC (collected at any time prior to Screening)
2. Evidence of cirrhosis including at least one of the following:
 - Biopsy results consistent with PBC Stage 4
 - Liver stiffness as assessed by TE Value ≥ 16.9 kPa
 - Clinical evidence in the absence of acute liver failure consistent with cirrhosis including: gastroesophageal varices, ascites, radiological evidence of cirrhosis (nodular liver or enlargement of portal vein and splenomegaly)
 - Combined low platelet count ($< 140\,000/\text{mm}^3$) with:
 - persistent decrease in serum albumin, or
 - elevation in prothrombin time /INR (not due to antithrombotic agent use), or
 - elevated bilirubin ($2 \times$ ULN)
3. Satisfy the criteria of the modified CP classification for hepatic impairment during Screening:
 - Moderate: CP-B (Scores 7 to 9) or
 - Severe: CP-C (Scores 10 to 12)
4. MELD score of 6 to 24 at Screening
5. Age ≥ 18 years
6. Taking UDCA for at least 12 months (stable dose for ≥ 3 months) prior to Day 1, or unable to tolerate or unresponsive to UDCA (no UDCA for ≥ 3 months)
7. Contraception: Female patients must be postmenopausal, surgically sterile, or if premenopausal (and not surgically sterile), be prepared to use ≥ 1 effective method of contraception during the study and for 30 days after the end of treatment visit. Effective methods of contraception are considered to be those listed below:
 - Barrier method, ie, (a) condom (male or female) with spermicide **or** (b) diaphragm with spermicide; or

- Intrauterine device; or
 - Vasectomy (partner); or
 - Hormonal (eg, contraceptive pill, patch, intramuscular implant or injection); or
 - Abstinence, if in line with the preferred and usual lifestyle of the patient (where abstinence is defined as refraining from heterosexual intercourse)

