15.4.2. Clinical Laboratory Evaluations

Laboratory parameters will be summarized in standard international (SI) system of units by treatment group using descriptive statistics at Baseline and at each on-study evaluation. Re-test or unscheduled results will not be summarized but will be included in the data listings. The change from Baseline will also be summarized. Baseline is defined as the mean of all available evaluations prior to treatment.

In addition, shift tables (ie, low-normal-high at Baseline versus low-normal-high at post Baseline visit in a 3-by-3 contingency table) from Baseline to worst value, last value, and at each scheduled post-Baseline visit will be provided for hematology and serum chemistry by treatment group to assess changes in laboratory values from Baseline to each on-study evaluation.

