15.6. Additional Efficacy Analyses

Analyses of changes in liver stiffness (TE) and liver fibrosis (ELF [HA, P3NP, and TIMP-1]) will be summarized and analyzed using the same methodology specified for the key secondary analyses of change in bilirubin.

The following clinical endpoints will be captured in the study:

- Time to death (all cause)
- Time to liver-related death
- Time to liver transplant
- MELD score ≥ 15 (for patients with MELD ≤ 12 at baseline)
- Hospitalization (as defined by a stay of 24 hours or greater) for new onset or recurrence of:
 - Time to variceal bleed
 - Time to hepatic encephalopathy (as defined by a West Haven score of ≥ 2)
 - Time to spontaneous bacterial peritonitis (confirmed by diagnostic paracentesis)
- Time to uncontrolled ascites (diuretic resistant ascites requiring therapeutic paracentesis at a frequency of at least twice in a month).

The incidence and time to first occurrence of any above listed clinical events will be summarized by treatment group using the log rank test stratified by the randomization stratification factor. KM estimates of the distribution of the time-to-event will be tabulated and graphed by treatment group. The tabulation will include the KM methodology using 25th, 50th (median), and 75th percentiles with associated 2-sided 95% confidence intervals (CIs), as well as percentage of censored observations. The number and percent of patients censored and with events will be presented. The hazard ratio and 2-sided 95% CI will be estimated based on a Cox regression model stratified by randomization strata.

In addition, the incidence and time to each of the above clinical events, and the incidence and time to occurrence of hepatocellular carcinoma (HCC) will be summarized by treatment group using the same methods as defined above.

Full details regarding additional efficacy analyses will be detailed in the SAP.

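### A baseline liver stiffness scan not needed for entry has no time limit and no pre-dose condition, so some patients may have an on-treatment baseline or none

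*Protocol*

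**What the plan says.** Table 1 (section 7.1.2) lists TE first at Day 1. It does not appear among the Screening procedures in section 9.7.4.

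Section 9.7.5 gives two fallbacks when TE cannot be done on Day 1:

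- Where the result bears on the cirrhosis assessment, "the procedure may be completed within the Day 1 Visit window, (if data is needed for cirrhosis assessment").
- Otherwise, it may be done "or as close as possible to the Day 1 Visit, preferably, after patient eligibility has been confirmed".

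The sentence that follows reads "Instruct the patient to take Day 1 dose on the day of this visit", and an earlier bullet in the same section says "Instruct the patient to begin dosing on the day of the Day 1 Visit". Neither makes the dose wait for a deferred scan. Table 1 footnote i orders things differently: "Patients will be instructed to begin dosing on Day 1, after completing all study assessments".

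TE has two uses in the trial:

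- **Entry.** "Liver stiffness as assessed by TE Value" of at least 16.9 kPa is one of several ways to show cirrhosis under inclusion criterion 2 (section 8.2).
- **Outcome.** Section 15.6 ("Analyses of changes in liver stiffness (TE) and liver fibrosis") applies the bilirubin method, which section 15.5 sets as ANCOVA of change to Week 48 with the baseline value as covariate.

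The one explicit analysis definition of baseline is in the laboratory section, 15.4.2: "Baseline is defined as the mean of all available evaluations prior to treatment". Section 15.7 rules out imputation.

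**The concern.** A baseline covariate should be measured before treatment can affect it. Under the second fallback a scan can fall days or weeks after the first dose and still comply with section 9.7.5. There are then two outcomes, and neither is good:

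- If the late scan is used as baseline, it already contains any early drug effect, in the OCA arm only. Adjusting for it removes that part of the effect from the treatment comparison.
- If the late scan is rejected as not pre-treatment, the patient has no change from baseline and, with no imputation, leaves the analysis.

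A later analysis plan can choose between these outcomes, but it cannot supply a pre-dose scan that was never taken. The protocol is therefore the place to settle the timing.

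**Working it through.** The plan states no figure for this point, so there is nothing to reproduce. The check is mainly a comparison of texts.

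**1. Is a post-dose scan permitted when TE is not needed for entry?** The second fallback gives no number of days, no direction relative to Day 1 and no pre-dose condition. Its stated preference is for a scan after eligibility is confirmed. Section 9.7.5 still has eligibility under review on Day 1, the day of randomisation and first dose, so that preference tends to push a deferred scan later. A post-dose scan is therefore permitted, though not required.

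**2. Is this consistent with the rest of the protocol?** No. Footnote i puts the first dose after all study assessments, whereas the fallback lets a Day 1 assessment happen afterwards. The ultrasound fallback in section 9.7.4 shows a bounded version: it may be done within the screening window or on Day 1, and results are reviewed against the exclusion criteria before randomisation. TE has no such bound.

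**3. What limits a scan needed for entry?** Section 9.7.5 allows randomisation only if all inclusion criteria are met, so such a scan has to come first. The time limit itself is missing. Section 9.7.1 refers to Table 1 for visit windows. Table 1 gives −28 to −14 days for Screening and ±1 week for Weeks 3 to 48, but the Day 1 cell is blank. Section 9.7.5 also lists the need for TE data to assess cirrhosis among the reasons a scan might not be done on Day 1, yet no earlier TE is scheduled.

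**4. Effect of using a late scan as baseline.** Let f be the share of OCA patients scanned late, δ the mean early drug effect on stiffness in those patients, and β the slope of the Week 48 value on baseline. The OCA baseline mean shifts by f × δ and the placebo mean does not. The adjusted difference moves by about −β × f × δ, so with a positive slope the early change is subtracted from the estimate whichever direction it takes. The protocol gives none of these quantities. A scan a few days late follows one 5 mg dose, so δ is probably small. With once-weekly dosing each further week adds a dose, and no cap is set.

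**5. Effect of dropping late scans.** About 50 patients randomised 1:1 (sections 7.2 and 15.2) gives 50/2 = 25 per arm. The standard error of a difference is proportional to √(2/n), so losing k per arm multiplies it by √(25/(25 − k)). The values of k are assumed.

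| k lost per arm | n left per arm | Multiplier | Increase in SE |
|---|---|---|---|
| 1 | 24 | √(25/24) = 1.02 | 2% |
| 3 | 22 | √(25/22) = 1.07 | 7% |
| 5 | 20 | √(25/20) = 1.12 | 12% |

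These losses would add to those at sites without the device, which section 14.2.1 allows for.

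**The case against.** A reader might infer that the scan may follow the first dose even when it is the evidence of cirrhosis for entry, so that a patient could be dosed with eligibility unconfirmed. The text does not support that. The open-ended clause is the alternative to the cirrhosis case, which is tied to the Day 1 window, and randomisation requires every inclusion criterion to be met. Randomising a patient whose only evidence of cirrhosis is a pending TE would breach the protocol. Section 9.7.3 also accepts other evidence of cirrhosis, including from medical history.

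Four further points can be made in the plan's defence:

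- **Direction.** The fallback also covers a scan before Day 1, so late scans are a possibility and not a certainty. This stands, and the point is worded accordingly.
- **Footnote i.** It can be read as already requiring the scan before dosing. But section 9.7.5 specifically provides for a scan on another day while telling the patient to dose on Day 1. The two need reconciling.
- **Blank window.** Day 1 is the anchor of the schedule, so an empty ± cell is not surprising in itself. It matters only because section 9.7.5 relies on a window that is defined nowhere.
- **Analysis plan.** The TE baseline definition and the handling of late scans are ordinary analysis-plan content; section 15.6 defers details there, and the definition in section 15.4.2 is written for laboratory values. That is fair for the analysis rule. It does not answer the timing rule, which determines whether a pre-dose value exists.

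**Conclusion.** The point holds for scans not needed for entry: section 9.7.5 permits an on-treatment or missing TE baseline and is inconsistent with Table 1 footnote i. For scans used for inclusion criterion 2, the remaining defect is narrower: an undefined Day 1 window and no TE scheduled at Screening.

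The consequence is small. Liver stiffness is an additional objective (section 6.3), no formal hypothesis is tested (section 15), and no stated sample size or primary analysis changes. The percentages above rest on assumed losses from 25 per arm and illustrate scale only, since the protocol gives no rate of late scans. This is an inexpensive improvement to the wording and does not threaten the trial's main conclusions.

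**What to change.** In section 9.7.5 and Table 1:

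1. At sites with the device, require the baseline TE at any time from Screening to pre-dose on Day 1.
2. Replace the undefined Day 1 window with that same period, and require the scan before randomisation when it is used for inclusion criterion 2.
3. Reconcile section 9.7.5 with Table 1 footnote i on the order of assessments and first dose.
4. State that a scan after the first dose is not a baseline value.

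The cost is a wording change and a few scans in patients who then fail screening. The existing 14 to 28 day screening period leaves room to schedule the scan.
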